### **3.3.3 Instructions on Missed Doses**

ONC201 can be given +/- **1 day** due to holidays, inclement weather, conflicts, or similar reasons. If the first dose of the 4-week cycle not taken within 1 day of day 1 of the cycle, the cycle will be delayed one week. If a mid-cycle dose (i.e., D8, D15, D22) is more than 1 day late, the weekly dose will be skipped and the next dose will be resumed in accordance with the planned administration day.

*Abbreviated Title: ONC201 in advanced cancers*  
*Version Date: 06/17/2020*

### 3.4 STUDY CALENDAR

Procedure	Screening/ Baseline	Cycle 1	Cycle 2	Subsequent Odd numbered cycles	Subsequent Even numbered cycles	End of treatment visit (~ 30 days from last dose)
		Day 1 (±3days)	Day 1 (±3days)	Day 1 (±3days)	Day 1 (±3days)	
Informed consent	X					
History and PE 	X	X	X	X	X	X
Vital signs	X	X	X	X	X	X
Performance Score	X	X	X	X	X	X
Labs	X 	X  (≤ 10 days)	X 	X 	X 	X 
Pathology confirmation 	X					
Tumor block	X 					
Fresh frozen tissue (tumor biopsy) 	X		X			X (optional)
Correlative Research Studies (blood samples)	X	X	X	X	X	X
PK/PD		X				
NIH Advance Directives Form	X (optional)					
Radiological Assessments 		X (≤ 17 days)		X		
Response Evaluation				X		

*Abbreviated Title: ONC201 in advanced cancers*

*Version Date: 06/17/2020*

Procedure	Screening/ Baseline	Cycle 1	Cycle 2	Subsequent Odd numbered cycles	Subsequent Even numbered cycles	End of treatment visit (~ 30 days from last dose)
		Day 1 (±3days)	Day 1 (±3days)	Day 1 (±3days)	Day 1 (±3days)	
Adverse Events		X	X	X	X	X
Concomitant Medications	X	X	X	X	X	X
Electrocardiogram 		X 	X			

 Up to 7 days before enrolling the trial

 History including prior treatments and review of baseline adverse events and concurrent medications. Physical examination includes neurological exam. Height (at screening only) and weight are also included.

 CBC with differential, PT/INR/PTT, AST (SGOT), ALT (SGPT), total protein, total bilirubin, serum creatinine. Urine or serum HCG on day of screening for women of childbearing potential. Anti-HIV, anti-HCV, Hepatitis B Surface Ag (within 28 days prior to first dose of study treatment).

 Labs must be obtained  $\leq 10$  days of initiating treatment: CBC with differential, PT/INR/PTT, sodium, potassium, chloride, carbon dioxide, BUN, creatinine or measured creatinine clearance, glucose, AST, ALT, bilirubin, calcium, total protein, albumin, alkaline phosphatase, phosphorus, magnesium, urinalysis, prolactin, estrogen, lactic acid and lipid panel. Lymphocyte phenotyping (TBNK). Urine or serum HCG for women of childbearing potential. Tumor Markers (CEA, CA15-3, CA27.29 for breast cancer and CA125 for endometrial cancer). Evaluation of germline BRCA1/2 (cohorts 1 and 2) or Lynch syndrome (germline evaluation) or MSI status of tumor (somatic evaluation by genomics, IHC or demonstration of Microsatellite instability of the tumor) (cohort 3) if no documentation of mutational analysis provided.

 Pathological confirmation of diagnosis (plus ER, PR and HER2 expression for breast cancer patients) in the Laboratory of Pathology at NIH Clinical Center or Walter Reed National Military Medical Center at Bethesda. However, if no pathologic specimen is available, patients may enroll with a pathologist's report showing a histologic diagnosis of HR+BC, TNBC or Endometrial Cancer in a College of American Pathologists (CAP) accredited laboratory and a clinical course consistent with the disease.

 Primary tumor paraffin block will be requested at enrollment to perform comparative genomic analysis as part of correlative studies planned for this clinical trial.

*Abbreviated Title: ONC201 in advanced cancers*

*Version Date: 06/17/2020*

 Planned biopsy after consent but prior to first dose of ONC201 as well as a planned biopsy on C2D2 after the 5th dose of ONC201. There is also an optional biopsy at the time of progression.

 Baseline images within 17 days prior to initiation of therapy: CT of chest/abdomen /pelvis (MRI may be substituted at investigator's discretion), Bone scan only at baseline. Brain MRI may be ordered at the discretion of the investigator if there is concern for CNS metastasis. CT of chest/abdomen/pelvis to be repeated every 8 weeks +/- 4 days after start of treatment (odd numbered cycles). Additional imaging to be performed at the investigator's discretion.

 12-lead EKG within 7 days prior to initiation of therapy and on C2D1, with monthly repeats only for abnormal baseline EKGs or if patient is symptomatic.

Note: Allowance for scheduling changes: Brief interruption and delay in the 28-day cycle may occasionally be required due to travel delays, airport closure, inclement weather, family responsibilities, security alerts and government holidays, etc., for scheduling convenience. This can also extend to complications of disease not attributable to disease progression or protocol therapy. These delays will not be considered protocol deviation.

*Abbreviated Title: ONC201 in advanced cancers*

*Version Date: 06/17/2020*

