## 1 INTRODUCTION

### 1.1 STUDY OBJECTIVES

#### 1.1.1 **Primary Objective**

- **Cohort 1 HR+BC** - To determine the progression free survival at 8 months (PFS by RECIST) of ONC201 in patients with refractory, metastatic hormone receptor positive breast cancer
- **Cohort 2 TNBC** - To determine the overall response rate (ORR; CR + PR by RECIST) of ONC201 in patients with metastatic triple negative breast cancer
- **Cohort 3 Endometrial Cancer** - To determine the ORR of ONC201 in patients with advanced or metastatic endometrial cancer

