### 3.3.2 Medication Delay

Hematologic AE on Day 1 of Each Cycle	
AE	Delay
ANC $< 1.0 \times 10^9 /L$ and/or Platelet count $< 75 \times 10^9 /L$	Delay up to 4 weeks until all resolved. If not resolved after 4 weeks, then remove from study regimen.

Non-Hematologic AE (except for controlled nausea, and vomiting) on Day 1 of Each Cycle (within the prior 72 hours)	
Grade	Delay

*Abbreviated Title: ONC201 in advanced cancers*

*Version Date: 06/17/2020*

2-4	Delay by 1 week up to 4 consecutive weeks until all resolved (to grade $\leq 1$ ). If not resolved after 4 weeks, then remove from study regimen.
-----	---------------------------------------------------------------------------------------------------------------------------------------------------

On day 1 of each cycle, patients must have adequate hematopoietic function (i.e., ANC  $\geq 1.0 \times 10^9$  /L, platelet count  $\geq 75 \times 10^9$  /L) and all grade 2, 3 or 4 non-hematologic AEs (except for controlled nausea, and vomiting) must have resolved to grade  $\leq 1$ .

If AEs persists, treatment should be delayed by 1 week for up to 4 consecutive weeks. If, after 4 weeks of delay, all treatment related AEs have still not resolved (to grade  $\leq 1$ ): then any further treatment with ONC201 should be stopped.

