### **6.3 RESPONSE CRITERIA**

For the purposes of this study, patients should be re-evaluated for response every 8 weeks +/- 4 days with imaging modalities determined appropriate by the investigators. In addition to a baseline scan, confirmatory scans should also be obtained 4 weeks +/- 4 days following initial documentation of objective response.

Response and progression will be evaluated in this study using the new international criteria proposed by the revised Response Evaluation Criteria in Solid Tumors (RECIST) guideline (version 1.1).(40) Changes in the largest diameter (unidimensional measurement) of the tumor lesions and the shortest diameter in the case of malignant lymph nodes are used in the RECIST criteria.

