### 10.2 SAMPLE SIZE DETERMINATION

#### Cohort 1: Refractory/recurrent metastatic HR+ breast cancer

Data from published trials indicate that the median PFS in patients with refractory/recurrent metastatic HR+ breast cancer is approximately 4 months. In this cohort, the goal is to determine if use of ONC201 is able to be associated with an 8-month median PFS probability (7, 8). With 24 evaluable patients receiving the proposed therapy, assuming accrual would take place over approximately 2 years, and that there would be at least 1 year of additional potential follow-up after the last patient has begun the therapy, there would be 80% power to determine whether there is a difference between a 4 month median PFS and an improved 8-month median PFS, with a one sided 0.10 alpha level test, using the method of Brookmeyer and Crowley (41). In practice, Kaplan-Meier curves and appropriate confidence intervals at selected time points will be provided to help interpret results relative to the expected results. As an early stopping rule, if 0 of the first 5 patients is able to be progression-free at 8 months, then no further patients will be accrued into this cohort as soon as that is able to be determined since the upper 95% one-sided confidence bound on 0/5 is

*Abbreviated Title: ONC201 in advanced cancers*

*Version Date: 06/17/2020*

45%, and thus this indicates inconsistency with an 8-month median PFS. The study may need to pause accrual to evaluate if PFS in any of the first 5 patients is  $\geq 8$  months.

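### Cohort 1's 8-month PFS falls between scheduled scans, and scans are tied to two clocks that part after a one-week cycle delay, so the estimate reads about 3 points high

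*Combined protocol and SAP*

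**What the plan says.** Section 1.1.1 sets the cohort 1 primary objective: "To determine the progression free survival at 8 months (PFS by RECIST) of ONC201". Section 10.2 builds an early stopping rule on the same point: accrual ends if none of the first 5 patients is progression-free at 8 months. A month is not defined in days or weeks.

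Scan timing is described in several places:

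- Section 6.3: "patients should be re-evaluated for response every 8 weeks +/- 4 days", a calendar schedule only.
- Section 3.4, footnote 8: "CT of chest/abdomen/pelvis to be repeated every 8 weeks +/- 4 days after start of treatment (odd numbered cycles"), a calendar schedule with a cycle label. The calendar table likewise puts imaging under Day 1 of odd-numbered cycles.
- Précis, Design: response every two cycles, equated with 8 weeks.

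Cycles can move. Under section 3.3.2, for persisting adverse events, "treatment should be delayed by 1 week for up to 4 consecutive weeks". Under section 3.3.3, if the first dose of a cycle is "not taken within 1 day of day 1 of the cycle, the cycle will be delayed one week". The note closing section 3.4 also allows scheduling delays without calling them deviations. Nothing says which clock governs the scan after a delay.

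Section 6.3.5 runs PFS from start of treatment to progression or death. It gives no rule for dating a progression found after the time point of interest, and no window for an 8-month assessment.

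**The concern.** Progression is normally seen only when someone looks. If no scan is due near the time point, the Kaplan-Meier curve there is mostly carried forward from the last scan. Patients who have progressed since then still count as progression-free. The error runs one way, in favour of the drug, in both the primary estimate and the futility check.

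The second clock adds to this. If scans follow cycles, a patient whose cycles are delayed, for toxicity among other reasons, is scanned later than one whose cycles are not. The time at which the primary endpoint is assessed then differs between patients for reasons linked to treatment.

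**Working it through.** **Inputs.** Section 10.2: "With 24 evaluable patients receiving the proposed therapy"; medians of 4 and 8 months; "a one sided 0.10 alpha level test, using the method of Brookmeyer and Crowley"; at least 1 year of follow-up after the last patient starts, so no administrative censoring before 8 months. Scan times come from sections 3.4 and 6.3. Assumptions: exponential PFS, S(t) = 0.5^(t/median), and 1 month = 365.25/12 = 30.4375 days = 4.348 weeks.

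**The plan's own figures.** The plan states that "there would be 80% power to determine whether there is a difference between a 4 month median PFS and an improved 8-month median PFS". Brookmeyer-Crowley tests S(4 months) = 0.5. Under an 8-month median, S(4 months) = 0.5^(4/8) = 0.7071. Power = Φ[(0.7071 − 0.5 − 1.2816·√(0.25/24)) / √(0.7071·0.2929/24)] = 79.4%, which agrees with 80%. The futility bound on 0/5 is 1 − 0.05^(1/5) = 45.1%, which agrees with the stated 45%.

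**Where 8 months falls.** 8 × 30.4375 = day 243.5 (week 34.8). The week-32 scan is day 224 ± 4, so days 220-228. The week-40 scan is day 280 ± 4, so days 276-284. Neither covers day 243.5. With 30-day months the point is day 240, also uncovered.

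**Size with no slip, no extra imaging and no death in the gap.**

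| Median | True S(8 months) | S(week 32) | Over the ± 4 day window | Excess |
|---|---|---|---|---|
| 4 months | 25.0% | 0.5^(32/17.39) = 27.9% | 27.3-28.6% | 2.9 points |
| 8 months | 50.0% | 0.5^(32/34.79) = 52.9% | 52.3-53.5% | 2.9 points |

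Deaths count when they occur. If a share d of the events between week 32 and week 34.8 are deaths, the excess is (1 − d) times the above. For d = 10-30% (assumed) it is 2.0-2.6 points.

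**Futility check.** The chance of 0/5 is (1 − S)^5. For a 4-month median it falls from 0.75^5 = 0.237 to 0.194. For an 8-month median it falls from 0.5^5 = 0.031 to 0.023.

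**The two clocks.** A one-week delay moves odd-cycle Day 1 by 7 days, beyond the 4-day tolerance, so one delay is enough for the two instructions to conflict. If scans follow cycles, the last scan before week 34.8 is as follows (slip taken as complete by cycle 7):

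| Total slip | Last scan | Excess, 4-month median | Excess, 8-month median |
|---|---|---|---|
| 0 weeks | week 32 | 2.9 | 2.9 |
| 1 week | week 33 | 1.8 | 1.8 |
| 2 weeks | week 34 | 0.8 | 0.8 |
| 3 weeks | week 27 | 9.1 | 8.4 |
| 4 weeks | week 28 | 7.8 | 7.2 |

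To average over patients, let each new cycle start one week late with probability p, independently. Let A ~ Bin(6, p) be the weeks of slip by cycle 7 and B ~ Bin(2, p) the further slip by cycle 9. The last scan before week 34.8 is at week 32 + A + B if A + B ≤ 2, and at week 24 + A otherwise. Averaging S over this for a 4-month median:

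| Assumed p | Recorded 8-month PFS (true 25.0%) | Cycle-9 scan after 8 months |
|---|---|---|
| 0 | 27.9% | 0% |
| 10% | 27.5% | 3.8% |
| 20% | 28.3% | 20% |
| 30% | 30.0% | 45% |

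The documents give no delay rate, so p is purely a range.

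**The case against.** The strongest reply is that the effect is small. About 3 points sits beside a 25-point contrast and a standard error of √(0.25·0.75/24) = 8.8 to √(0.5·0.5/24) = 10.2 points. This stands, and it limits the weight of the point. The excess is nonetheless systematic and is removed by wording.

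A second reply is that a month could mean 28 days, which puts 8 months on the week-32 scan. The documents do not say so, and it would not cure the problem. Day 224 is then mid-window, and patients scanned on days 225-228 would still carry their week-24 result. With scan days spread evenly over days 220-228 (assumed) and medians also in 28-day months, recorded PFS at a 4-month median is (5 × 25.3% + 4 × 35.4%)/9 = 29.8%, against 25.0%.

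Third, footnote 8 allows discretionary imaging and section 6.3 asks for confirmatory scans. Discretionary scans can shrink the excess. Confirmatory scans do so rarely: on the calendar schedule, those following the week-24 and week-32 scans fall by day 172 + 32 = 204 or from day 220 + 24 = 244, either side of the gap.

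Fourth, the odd-cycle parenthesis may only name a calendar column, since section 6.3 is purely calendar-based. That is a fair reading, but the calendar table and the précis point the other way, and no text settles it.

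A reader might infer that the reported figure simply is week-32 PFS for everyone. The documents do not support that. Deaths count when they occur, extra imaging is allowed, and if scans follow cycles the effective time runs from week 27 to week 34. A reader might also infer that toxicity delays make the bias much worse. At a 10% delay rate it is slightly smaller than with no delay, because a slip of one or two weeks moves the scan towards 8 months. It grows only at higher rates, which the documents neither give nor suggest.

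**Conclusion.** The point holds as a modest defect with a cheap remedy. No scheduled scan window covers 8 calendar months, and the two scan clocks conflict after one one-week delay. With no slip, extra imaging or death in the gap, the 8-month estimate reads about 2.9 points high under either median. It is 2.0-2.6 points high if 10-30% of the gap's events are deaths. If scans follow cycles, the recorded value at a 4-month median is 27.5-30.0% for assumed delay probabilities of 10-30% per cycle. These sizes rest on exponential PFS and calendar months.

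Three further inferences go beyond the documents:

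- **Power.** The stated 80% reproduces. It belongs to a test of the median and is not challenged here.
- **Bias against the historical 4-month median.** If the published trials also dated progression at scans, part of the excess is shared. The documents do not show how that median was measured, so net bias cannot be judged.
- **A false-positive rate at 8 months.** Section 10.4 plans descriptive estimates with confidence intervals, and cohort 1 has no success rule based on the number progression-free at 8 months, so there is no such error rate to quote.

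**What to change.** 1. In section 3.4 footnote 8, state that scans are due every 8 weeks ± 4 days from Cycle 1 Day 1, whatever the cycle number or dose delay. Delete the odd-cycle parenthesis. Bring the section 3.4 calendar table and the précis Design text into line with section 6.3.
2. In sections 1.1.1, 10.1, 10.2 and 10.4.2 and the précis objectives, define the cohort 1 estimate as PFS at the week-32 assessment including its window, read just after day 228. Use the same definition for the 0-of-5 check.
3. Give reference values at that time: 27.9% and 52.9% for medians of 4 and 8 months (27.3-28.6% and 52.3-53.5% over the window), labelled as assuming exponential PFS.

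The cost is wording only, with the same number of scans. The downsides are that the endpoint is labelled week 32 instead of 8 months, and that after a cycle delay some scans will no longer coincide with a Day 1 visit.

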### 3.5 CRITERIA FOR REMOVAL FROM PROTOCOL THERAPY AND OFF STUDY CRITERIA

Prior to removal from study, effort must be made to have all subjects complete a safety visit approximately 30 days following the last dose of study therapy.

#### 3.5.1 **Criteria for removal from protocol therapy**

- Progressive disease
- Participant requests to be withdrawn from active therapy
- Unacceptable Toxicity as defined in section 3.3.
- Investigator discretion
- Positive pregnancy test

#### 3.5.2 **Off-Study Criteria**

- Screen Failure
- Completed study follow-up period
- Study closure
- Participant requests to be withdrawn from study
- Death

## 4 CONCOMITANT MEDICATIONS/MEASURES

The investigator's brochure for ONC201 by Oncoceutics does not describe any known drug-drug interactions with ONC201. In vitro cytochrome P450 assays were conducted in human hepatocytes. In these studies, ONC201 is not an inducer of the CYP450 system (CYP1A2, 2B6, and 3A4). ONC201 was observed to be a mild inhibitor of the CYP450 enzymes (1A2, 2B6, 2C8, 2C9, 2C19, 2D6, 3A4) at 35-429 uM, i.e., at least 3.5-fold above the Cmax observed in the first-in-human trial.

Drugs that antagonize DRD2 are commonly used as antipsychotics. However, comparison between ONC201 and other typical antipsychotics (such as haloperidol and risperidone) reveal substantial differences in anti-tumor activity, therapeutic window, specificity and receptor pharmacology. Moreover, the current administration schedule of ONC201 dosing is atypical for antipsychotic drugs. Taken together, there is no clear expectation that side effects that are commonly observed with antipsychotic drugs will be observed with ONC201 in the current schedule. Nevertheless, it is possible that side effects associated with antipsychotics could be observed with ONC201 including weight gain, diabetes, metabolic disorders, dystonia, akinesia, akathisia, tremors, muscle rigidity, insomnia, blurry vision, Parkinsonian symptoms, cognitive impairment, sexual dysfunction, osteoporosis, sedation, behavioral changes, and cardiac disorders.

*Abbreviated Title: ONC201 in advanced cancers*

*Version Date: 06/17/2020*

#### 4.1 RESTRICTIONS

As a general precaution, the use of metformin and similars are prohibited due to potential similarities in mechanisms and mitochondrial damage. Patients will also be prohibited from using herbs and magic potions.

##### **Breast feeding**

It is not known whether ONC201 is excreted in breast milk. It is recommended that women do not breastfeed during treatment with ONC201 and for at least 2 months after the last dose.

##### **Blood Donation**

Patients should not donate blood while participating in this study or for 90 days following the dose of ONC201.

#### 4.2 CONTRACEPTION

The effects of ONC201 on the developing human fetus are unknown. For this reason, women of childbearing potential and men must agree to use two methods of adequate contraception (see [Table 3](#)) prior to study entry, for the duration of study participation and for at least 4 weeks after the final dose of any study-related medications. Cessation of birth control after this point should be discussed with a responsible physician. Periodic abstinence, the rhythm method and the withdrawal method are not acceptable methods of birth control.

Table 3: Effective methods of contraception (two methods must be used)

Barrier Methods	Intrauterine Device Methods	Hormonal Methods
Male condom plus spermicide	Copper T	Implants
Cap plus spermicide	Progesterone T a	Hormone shot or injection
Diaphragm plus spermicide	Levonorgestrel-releasing intrauterine system (e.g., Mirena)	Combined pill
		Minipill
		Patch

aThis is also considered a hormonal method of birth control

## 5 BIOSPECIMEN COLLECTION

### 5.1 CORRELATIVE STUDIES FOR RESEARCH/PHARMACOKINETIC STUDIES

The primary goal of the correlative studies is to identify potential predictive biomarkers as well as additional evidence of the mechanism of action of and resistance to ONC201. Other correlative study aims include investigation of proof-of-concept biomarkers. These will be

*Abbreviated Title: ONC201 in advanced cancers*

*Version Date: 06/17/2020*

performed in an exploratory fashion on select patients if there are adequate samples for analysis. (**Table 4**; **Table 5**)

While the exact mechanism of ONC201 is unclear at this time, preclinical data as well as the phase I data have identified multiple potential mechanisms of action. As mentioned above, ONC201 is thought to have both TRAIL-dependent and TRAIL-independent mechanisms of killing. ONC201 has been identified as a selective antagonist of DRD2 that activates the integrated stress response in tumor cells leading to TRAIL activation. Serum prolactin will be evaluated as a surrogate marker for target engagement, which is induced by DRD2 antagonism in the pituitary gland (34). In the solid tumor phase I study, prolactin was found to increase in patients taking ONC201 and was loosely associated with response in the small trial. However, there is no evidence that DRD2 is present on tumors. In addition to serum prolactin levels, we will also evaluate select biopsy samples for the presence of DRD2.

ONC201 has shown TRAIL-dependent apoptosis as well as caspase-independent, DR4/5-independent, TRAIL-independent induction of the integrated stress response through inhibition of mitochondrial respiration. Due to these conflicting mechanisms, we will evaluate select tissue biopsy samples for markers of apoptosis including cleaved caspase-3, cleaved poly(ADP ribose) polymerase (PARP), cleaved terminal deoxynucleotidyl transferase dUPT nick end labeling (TUNEL), ATF4 expression, CHOP expression, phospho-AMPK levels, annexin-V, TRAIL receptor and TRAIL expression. We will also evaluate markers of apoptosis in the serum including TRAIL expression, M30 assays, and M65 assays. We also plan to evaluate serum cytokine levels including IL6, L24, IL32, IL1RAP, which were found to be increased after ONC201 administration on RNAseq.

